## **1. BACKGROUND/RATIONALE**

Psoriasis is a prevalent global skin disease (1). Psoriasis is not simply an inflammatory disease of the skin but also a systemic inflammatory condition that carries a higher risk for cardiovascular disease and other systemic comorbidities. Certain inflammatory markers are known to be elevated in the serum of patients with psoriasis. Some of these markers may correlate with severity and extent of skin lesions (i.e. PASI score), while others may not (2). Therapies that decrease the inflammation present in the skin could lead to a systemic decrease in inflammatory mediators, thereby lowering the risk for developing comorbidities. UVB phototherapy has been employed in the treatment of psoriasis for decades. The UVB wavelengths most effective for psoriasis (i.e. action spectrum) falls within 308-313 nm. Narrowband UVB (311 nm) is the most popular phototherapeutic modality for full body treatment, in which unaffected normal skin is also exposed to UV light. Lesion targeted NUVB became feasible upon the introduction of 308 nm excimer lasers. This strategy not only spared normal skin from unnecessary UV, but also allowed for higher doses of UV to be delivered on lesional skin, within a reasonable amount of time. Currently, excimer laser treatment of psoriasis is an FDA-approved therapy. Whereas changes in serum resistin have been demonstrated after NUVB (3), there is no data regarding targeted UVB excimer laser treatments and serum inflammatory markers.

Hyperpigmentation is a common adverse effect reported after targeted UVB phototherapy (4,5). In our clinical experience, the Photomedex Xtrac® Velocity Excimer Laser has resulted in minimal to no hyperpigmentation after psoriasis plaque treatment. Furthermore, there is a lack of research objectively measuring hyperpigmentation and erythema after excimer laser treatment.

## **2. STUDY OBJECTIVES/HYPOTHESIS**

The overall aims for this study are to determine whether UVB excimer laser treatment of psoriasis affects serum inflammatory markers, and to assess hyperpigmentation and erythema with excimer laser treatment.

We hypothesize that treatment of psoriasis with UVB delivered via 308 nm excimer laser will decrease the levels of serum inflammatory markers. We hypothesize that treatment will decrease plaque erythema and will result in minimal hyperpigmentation

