## **3. STUDY DESIGN**

We plan on enrolling 24-27 psoriasis patients for this research study.

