### **3.1 STUDY POPULATION**

#### **3.1.1 Inclusion Criteria**

- Age 18 years and older
- Male or female with diagnosis of psoriasis
- Psoriasis involvement of 5-15% BSA
- Has been off systemic psoriasis therapies (e.g. retinoids, methotrexate, biologic agents, etc) for at least 4 weeks
- Has been off topical therapies (e.g. calcipotriene, topical steroids) for at least 2 weeks
- Fitzpatrick Skin Types I-VI

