**University Hospitals Case Medical Center**  
**Department of Dermatology**  
**Protocol**

**Protocol Title:** Effects of UVB Excimer Laser on Serum Inflammatory Markers in Patients with Psoriasis

**Principal Investigator:** [name], NP

**Co-Principal Investigator:** [name]

**3.2.6 Chromameter Assessment:** Treated plaques will be evaluated using a chromameter as an objective measure of hyperpigmentation and erythema at Screening Visit, Visit 8, Visit 16, Visit 23 Final/Early Termination Visit, and, if applicable, the 3 month follow-up visit. The chromameter uses the L\*a\*b\* color system. L\* measures skin reflectance or lightness, a\* measures red to green color saturation, b\* measures yellow to blue color saturation. Hyperpigmentation of treated plaques will be assessed via L\*. L\* values of treated plaques will be compared to L\* values of normal, untreated skin. Erythema of treated plaques will be assessed via a\*. a\* values of treated plaques will be compared to a\* values of normal, untreated skin. These values will also be compared from visit to visit.

**3.2.7 Limited Medical Exam:** Medical and Dermatological history, demographic information, concomitant medications, vital signs, height, weight, and BMI will be collected during Visit 1/Screening Visit.

**3.2.8 Blood Draw:** Blood will be drawn at Visit 1/Screening Visit and at Visit 23 Final/Early Termination Visit by venipuncture and will be evaluated for:

- Serum Inflammatory Markers: (e.g. Levels of CRP, resistin, MPO and S100, etc) as quantified via ELISA kits [ $\sim$ 10mL blood].
- Pro-Inflammatory Monocytes (optional): Populations of monocytes will be characterized in the blood and via flow cytometry analysis [ $\sim$ 60mL blood].

**3.2.9 Questionnaires:** Subjects will be asked to complete two questionnaires.

**3.2.5.1 Patient Satisfaction Survey:** Patients will be asked to complete a survey, scoring their satisfaction with the treatment at Visit 23 Final/Early Termination Visit.

**3.2.5.2 Nutrition Questionnaire:** Patients will be asked to complete a survey about their nutritional habits at Visit 1/Screening Visit.

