### **3.3 STUDY VISITS**

#### **3.3.1 Visit 1: Screening Visit (estimated time: ~ 90 minutes)**

- Subjects will review the Institutional Review Board (IRB) approved Informed Consent Form (ICF) with the study staff. After all study procedures have been discussed and all questions have been answered, subjects will affirm participation by signing and dating the consent form.
- Inclusion/exclusion criteria will be reviewed and subject eligibility confirmed.
- Study staff will review concomitant medications and procedures with each subject.
- Medical and Dermatological History information will be collected.
- Vital signs, height, weight and BMI will be collected and recorded.
- Subjects will have their psoriasis clinically evaluated through PASI scoring and PGA.
- A chromameter will be used to evaluate pigmentation before treatment.
- Subjects will have plaque/body photographs taken
- Subjects will undergo a Sunburn MED Test or Visual MED Test.
- Subjects will complete a dietary/nutrition questionnaire.
- Subjects will undergo a pre-treatment blood draw.
- An optional, pre-treatment punch biopsy may be taken from a psoriasis lesion.

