#### **3.3.3 Treatment Visits (Visits 3-22) (estimated time: up to 1 hour):**

***\*Patients will undergo Treatment twice a week until they reach a PASI 75 improvement, or until they reach the maximum of 20 total treatments\****

- Study staff will review concomitant medications, any AEs since the previous visit, and procedures with each subject.
- Subjects will have their psoriasis clinically evaluated through PASI scoring and PGA every four weeks during Visit 8 and Visit 16.
- During Visit 8 and Visit 16, treated plaques will be evaluated using a chromameter to measure hyperpigmentation and erythema that may be caused by the laser.
- Subjects will have plaque/body photographs throughout this study.
- Subjects will undergo standard clinical treatment with an Excimer Laser.

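### Section 2 sets a causal aim for serum markers, but two draws in one treated group can only estimate a before-to-after change

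*Combined protocol and SAP*

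**What the plan says.** All references are to the combined protocol and SAP.

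- **Aim (section 2):** "to determine whether UVB excimer laser treatment of psoriasis affects serum inflammatory markers".
- **First hypothesis (section 2):** "treatment of psoriasis with UVB delivered via 308 nm excimer laser will decrease the levels of serum inflammatory markers".
- **Size (section 3):** "We plan on enrolling 24-27 psoriasis patients for this research study". No arms, allocation or sample-size reasoning are given.
- **Treatment (section 3.3.3):** "Patients will undergo Treatment twice a week until they reach a PASI 75 improvement, or until they reach the maximum of 20 total treatments". No sham, untreated, delayed-start or randomised group appears anywhere.
- **Serum sampling (section 3.2.8):** "Blood will be drawn at Visit 1/Screening Visit and at Visit 23 Final/Early Termination Visit by venipuncture". The baseline sample is taken at the visit where eligibility is confirmed (section 3.3.1: "Subjects will undergo a pre-treatment blood draw"). The optional 3-month visit has no draw (sections 3.3.5 and 3.4).
- **Entry (section 3.1.1):** body surface involvement of 5-15%, at least 4 weeks off systemic psoriasis therapy, and, for topical therapy, "Has been off topical therapies (e.g. calcipotriene, topical steroids) for at least 2 weeks". There is no marker threshold, stable-disease requirement or run-in.
- **Analysis (section 14.2):** markers are measured before and after treatment and related by regression to PASI, number of treatments, BMI and nutrition data. No test or interval for the before-to-after change is named.

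**The concern.** The verb in the aim and the direction of the hypothesis both call for attribution: the laser changes the markers. Attribution needs some view of what the markers would have done over the same weeks without the laser, and nothing in the plan supplies one for serum. For skin colour, by contrast, treated plaques are compared with normal, untreated skin (sections 3.2.6 and 14.4).

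What is at stake is the conclusion the study may draw. Section 1 says there are no data on excimer laser and serum markers, and suggests that lowering systemic mediators could lower comorbidity risk. In a first report, a fall stated in the terms of the aim would claim more than the data can carry, and nothing in section 14 limits the claim.

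**Working it through.** The plan gives no power, alpha, effect size or SD, so there is no planned figure to reproduce. The check asks what the two draws can identify.

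**1. What the observed change contains.** For any marker, write the mean change (Visit 23 minus screening) as

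D = L + F + R + W

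where L is the laser effect, F is natural fluctuation shared by the group over the period, R is regression to the mean and W is the effect of having stopped earlier therapy. The plan yields one number, D, for four unknowns. A concurrent control would estimate F + R + W and allow subtraction. Repeat baseline draws would show part of R and W. The plan has neither.

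**2. Can the other terms be bounded from the documents?**
- *R.* If the group enters k SD above its source-population mean and the test-retest correlation is r, then R = -(1 - r)k SD. Neither r nor k is in the documents. The sign of k is not fixed either: entry is on surface area, with a floor and a ceiling, and section 1 says some markers may track severity while others may not.
- *W.* A flare that subsides after screening lowers the second reading; one still building raises it. W is zero for patients with no recent therapy. The washouts are minimum periods, so the mix of patients is unknown.
- *F.* Nothing in the documents bears on its size.

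**3. Do the regressions in section 14.2 recover L?**
- *PASI.* If psoriasis improves spontaneously, PASI and any marker that tracks it fall together. An association between the two is expected whether or not the laser acts on the marker.
- *Number of treatments.* This is not an independently set dose, because treatment stops at PASI 75. Visits 3-22 are 22 - 3 + 1 = 20 treatments, or 20 / 2 = 10 weeks at two a week. The scheduled PASI assessments fall at treatment 8 - 2 = 6 (about 3 weeks) and 16 - 2 = 14 (about 7 weeks). If PASI 75 is judged at those visits and no session is skipped, a responder has about 3 or 7 weeks of treatment and a non-responder about 10, with the final draw 2 days to 2 weeks later. Response therefore sets both the treatment count and the time between draws. In responders the second draw also follows soon after a good PASI reading.
- *BMI and nutrition.* Both are recorded at screening only. They may explain differences between patients but say nothing about an untreated course.

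**4. Could the present sample be split to create a control?** Assume two-sided 5% alpha, 80% power and the normal approximation; none of these is in the plan. Let d be the difference in mean change in SD units. Then n per arm = 2(1.96 + 0.84)² / d² ≈ 15.7 / d².
- d = 0.5: 15.7 / 0.25 ≈ 63 per arm.
- d = 0.8: 15.7 / 0.64 ≈ 25 per arm.
- 12 per arm: d ≈ √(15.7 / 12) ≈ 1.14. 13 per arm: d ≈ √(15.7 / 13) ≈ 1.10.

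Splitting 24-27 patients would reveal only very large effects, so changing the claim is the realistic remedy.

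**5. What the design can deliver.** If all patients give both samples, a 95% interval for the mean change has half-width t/√n in SDs of the change: 2.07 / √24 ≈ 0.42 for 24 patients and 2.06 / √27 ≈ 0.40 for 27. That is usable as a first description.

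**The case against.** The best defence is that this is a small exploratory study in an area without data, for which an uncontrolled before-and-after design is an ordinary choice. Section 14 speaks mainly of descriptive statistics and correlation, and section 1 puts the comorbidity link conditionally. That stands. The design need not change, and no passage commits the sponsor to publishing a causal conclusion. It does not remove the mismatch, because section 2 still states the aim and hypothesis causally.

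Three stronger readings are tempting, and the documents do not support them.

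- *Patients enter at their worst, so some fall is expected without any laser effect.* The plan does not say this. Patients above 15% surface area are excluded as well as those below 5%, no marker is used for selection, and a washout effect could hide a benefit as easily as imitate one.
- *A false-positive rate can be put on the problem.* That needs values for r and k, a paired test and an alpha, and the plan gives none of them. The answer also turns on what k means: measured from the population mean, the expected fall is (1 - r)k; measured from patients' own usual level, to which they return, it is k. A percentage would reflect the assumptions and not the trial.
- *Relating marker change to time since last therapy would expose a flare.* No last-dose date is specified for collection, the variable is undefined for never-treated patients, it does not address regression to the mean, and with 24-27 patients it could not identify flare recovery.

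**Conclusion.** The point holds as a mismatch between claim and design. One treated group with one serum draw before and one after can estimate how much markers changed over a course of excimer laser. It cannot determine whether the laser caused the change, and the planned regressions do not close the gap. The size of any bias is not computable from the documents, and its direction could be either way.

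The conclusion rests on reading the study as single-arm. The plan never names its design, but every described procedure treats every patient. It does not depend on any assumed correlation, baseline elevation or significance test. It should be corrected because it governs what the study may conclude; it is no reason to think the study not worth doing.

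**What to change.** 1. **Section 2:** restate the serum part of the aim, and the first hypothesis, as estimating the change in serum inflammatory markers from before to after a course of excimer laser.
2. **Section 14.2:** state that the within-patient change in each marker will be reported with a confidence interval and will not be attributed causally to the laser.

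This needs no control arm, visit or blood draw beyond those planned. The cost is a short rewording of section 2, a sentence or two in section 14.2, and a weaker stated claim.

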## **3. STUDY DESIGN**

We plan on enrolling 24-27 psoriasis patients for this research study.

### **3.1 STUDY POPULATION**

#### **3.1.1 Inclusion Criteria**

- Age 18 years and older
- Male or female with diagnosis of psoriasis
- Psoriasis involvement of 5-15% BSA
- Has been off systemic psoriasis therapies (e.g. retinoids, methotrexate, biologic agents, etc) for at least 4 weeks
- Has been off topical therapies (e.g. calcipotriene, topical steroids) for at least 2 weeks
- Fitzpatrick Skin Types I-VI

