#### **3.1.2 Exclusion Criteria**

- Active history of photosensitivity (e.g. xeroderma pigmentosum, lupus erythematosus, porphyria, severe polymorphous light eruption, solar urticaria)
- Any suspicion that the psoriasis is of the photosensitive variant.
- Any medical condition that could be aggravated or may cause extreme discomfort during the study period.

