**8. ALTERNATIVES TO PARTICIPATION**

Alternative treatments available to patients who decide not to participate or who may withdraw early from the study are:

- Topical creams/ointments
- Methotrexate
- Oral retinoids
- Cyclosporine
- Full body narrowband UVB
- Biologics

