#### **16. PLANS FOR THE SUBJECTS AT THE END OF THE PROTOCOL**

At the last visit, patients will be advised that lesions that do not demonstrate improvement should be treated using other established therapies (e.g. topical steroids, retinoids, phototherapy, etc), and appropriate referrals will be made.

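### The washout list does not name phototherapy, so recent UVB treatment could already have altered baseline resistin and skin colour; how much this matters is unknown

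*Combined protocol and SAP*

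**What the plan says.** Section 3.1.1 has two washout criteria. The first is "Has been off systemic psoriasis therapies (e.g. retinoids, methotrexate, biologic agents, etc) for at least 4 weeks". The second is "Has been off topical therapies (e.g. calcipotriene, topical steroids) for at least 2 weeks". Every named example in both is a drug.

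The only light-related exclusions in Section 3.1.2 concern photosensitivity: "Active history of photosensitivity (e.g. xeroderma pigmentosum, lupus erythematosus, porphyria, severe polymorphous light eruption, solar urticaria", and suspicion of the photosensitive variant of psoriasis. Neither refers to recent UV treatment.

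Section 3.3.1 has staff review medications and procedures and take a dermatological history at Visit 1, but attaches no rule about phototherapy to either. Eligibility, baseline blood and baseline chromameter readings all belong to that same visit. Section 14 does not adjust for earlier UV exposure.

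Section 1 supplies three relevant premises:
- on serum, "Whereas changes in serum resistin have been demonstrated after NUVB (3";
- on skin colour, "Hyperpigmentation is a common adverse effect reported after targeted UVB phototherapy (4,5";
- on whole-body narrowband UVB, that it is a treatment "in which unaffected normal skin is also exposed to UV light".

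Phototherapy is also a realistic prior treatment for these patients. Section 8 lists "Full body narrowband UVB" among the alternatives, and the end-of-protocol section refers to "other established therapies (e.g. topical steroids, retinoids, phototherapy, etc".

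**The concern.** The protocol accepts that recent psoriasis treatment must be cleared before baseline, yet does not name the class of treatment it is studying. The study as described follows one treated group from screening to the final visit, with no control group in which carryover would show itself.

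Two outcomes are exposed. Resistin is a named marker, and the hypothesis in Section 2 is a fall. If earlier UVB has already lowered it, less of the fall remains to be seen. Skin colour is read by chromameter as L\* and a\* on treated plaques, against normal untreated skin and from visit to visit. Earlier phototherapy may have changed plaque colour at baseline and, if it was whole-body, the reference skin as well.

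**Working it through.** **Does any text close the gap?**

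| Place | What it restricts | Prior phototherapy restricted? |
|---|---|---|
| 3.1.1, systemic | Drugs, then *etc*; 4 weeks | Targeted: no. Whole-body: ambiguous |
| 3.1.1, topical | Calcipotriene and topical steroids as examples; 2 weeks | No |
| 3.1.2 | Photosensitivity; conditions that could be aggravated or cause extreme discomfort | No |
| 3.3.1 | History and procedures are recorded | No rule attached |
| 14.2, 14.4 | Analysis | No adjustment |

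**Which outcomes are reached, on the protocol's own premises?**

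- *Resistin.* Section 1 reports a change after narrowband UVB, and the title of reference 3 gives the direction as a reduction. Section 1 also says there are no data on excimer laser and serum markers. The premise is therefore for 311 nm UVB and covers one of the four named markers (CRP, resistin, MPO, S100).
- *Plaque colour.* Section 1 says hyperpigmentation is common after targeted UVB, so earlier targeted treatment can alter baseline plaque readings.
- *Reference skin.* Section 1 says whole-body narrowband UVB reaches normal skin and targeted treatment spares it. Only whole-body UV would therefore alter the normal-skin reference.

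**How large could the resistin effect be?** The plan has no sample size calculation to reproduce. Section 3 gives 24-27 patients without an effect size, SD, alpha or power, and Section 14.2 names no paired test. Everything below except the patient numbers is an assumption.

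1. Take a paired t-test, two-sided 5%, 80% power. The detectable standardised change is about 0.60 SD at n = 24 and 0.56 SD at n = 27. The normal approximation (1.960 + 0.842)/√n gives 0.57 and 0.54.
2. Let p be the share of patients with recent UVB and r the share of the effect already present at their baseline. With d = 0.60 and a within-group SD of 1:
   - mean change = d(1 − pr);
   - variance = 1 + d²r²p(1 − p);
   - standardised change = mean/√variance;
   - power from the noncentral t with n − 1 degrees of freedom and noncentrality √n × standardised change.
3. Example, p = 0.20 and r = 0.5: mean 0.60 × 0.90 = 0.54; variance 1 + 0.36 × 0.25 × 0.16 = 1.0144; standardised change 0.536; power 71%.
4. Example, p = 0.20 and r = 1: mean 0.60 × 0.80 = 0.48; variance 1 + 0.36 × 0.16 = 1.0576; standardised change 0.467; power 59%.

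| Share affected (n = 24) | Half present at baseline | All present at baseline |
|---|---|---|
| 0% | 80% | 80% |
| 10% (about 2 patients) | 76% | 70% |
| 20% (about 5) | 71% | 59% |
| 30% (about 7) | 66% | 48% |

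With n = 27 and 0.56 SD, the figures are the same to the nearest point. A single affected patient in 24 leaves power at about 76% even with full carryover.

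**The case against.** The best defence is that the systemic criterion ends in *etc*, and that phototherapy's separate listing elsewhere proves little. Section 8 is a flat list in which methotrexate, oral retinoids, cyclosporine and biologics each have their own line. Cyclosporine is also unnamed in Section 3.1.1, yet plainly falls under *etc*. This stands as far as it goes. A reader might infer that whole-body UVB in the week before screening is definitely permitted, but the text supports only ambiguity. For targeted excimer treatment the defence fails, because that is neither a systemic nor a topical therapy.

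A second objection concerns size. A reader might infer that power would fall to 48%, or that the serum results as a whole are compromised. The documents support neither. The 48% needs 30% of patients affected and the whole effect already spent. The test and effect size are not in the plan, and the documents give no UVB effect on CRP, MPO or S100. Nor do they say how long a resistin effect lasts.

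A third concerns colour. It is tempting to say that earlier UV biases the L\* contrast in a known direction. Earlier targeted treatment would not tan the reference skin. Whole-body UV would reach plaque and reference alike, so part of the contrast may cancel. Section 4.1 adds that colour change from MED testing can, at the extreme, take over a year to even out, so a washout may reduce this problem without removing it.

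These objections limit the size of the point. They do not supply the missing criterion.

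**Conclusion.** The omission is a fact of the text. Recent targeted excimer treatment is no bar to entry, and the position of whole-body UVB is unclear. On the protocol's own premises, such a patient could have an altered baseline for resistin and plaque colour and, after whole-body UV, for the normal-skin L\* and a\* reference.

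The likely consequence for resistin is an understated fall. This assumes that the 311 nm finding carries over to the patient's earlier treatment and that some of the effect persists at screening. The illustrative power range runs from 80% (none affected) to 48% (30% affected, full carryover). No point within it can be called likely, because the documents give neither prevalence nor persistence. For the L\* contrast, neither direction nor size is established.

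This is an inexpensive improvement worth making. It is not evidence that the results will be biased.

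**What to change.** 1. In Section 3.1.1, name phototherapy, both whole-body and targeted, in the washout list, with a window the investigators set. This also settles how *etc* is to be read.
2. Record the date of last phototherapy in the dermatological history already taken at Visit 1.
3. Only if enrolment has already begun without the criterion, use that date for a sensitivity analysis in Sections 14.2 and 14.4 that excludes patients with exposure inside the window. Once the criterion is in force, such an analysis would exclude almost nobody and is not needed.

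The cost is one line of eligibility text and one history item. A few candidates may have to wait before screening.
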